6.2 Data Security

Our research team employs standard procedures to ensure confidential information about study participation is not disclosed. All data are linked to an arbitrary 3-digit study ID unrelated to personal information. The file linking participants to their study ID will be stored in a password-protected file, located within a password-protected database on an encrypted computer. Only select trained laboratory personnel will have access to the file. All computer files or printed data used for analysis also will be de-identified. Informed consent collected remotely will be stored in HIPAA compatible survey platform, RedCap. Physical consent forms or other forms with identifiable information be stored in a locked file cabinet separate from data in an office that is locked when not occupied.

All technology platforms handling PHI will be HIPAA compatible and our team is well trained in HIPAA compliance.

6.3 Data and Safety Monitoring

A. Periodic Data Evaluation

A Data Safety Monitoring Board will meet quarterly to evaluate safety data and other study issues.

B. Type of Data Evaluated

Safety data will be reviewed quarterly. Efficacy data will be evaluated after 50% of participants have completed follow-up data collection.

C. Collection of Safety Information

We will use case report forms to document adverse events at each telehealth patient contact.

D. Frequency of Data Collection

We will document adverse events at each telehealth patient contact.

E. Reviewer of Data

A Data Safety Monitoring Board will meet quarterly to evaluate safety data and other study issues. The PI ([name]) and medical monitor (Co: [name]) will review safety data as it is collected.

F. Schedule of Review of Cumulative Data

Safety data will be reviewed every 6-months.

G. Tests for Safety Data

Independent t-tests will be used to examine differences between treatment groups with respect to number of adverse events reported.

H. Suspension of Research

We do not expect any adverse events in this trial that would indicate stopping the trial because we are providing established treatments to smokers trying to quit. We will monitor adverse events, however, and stop the trial if our DSMB determines that it is warranted in response to adverse events.

In addition, we will stop the trial if the DSMB concludes that interim analysis at the halfway point of the trial provided overwhelming evidence that PTSC-S intervention was more efficacious than the control intervention.

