1.3 Research Design and Methods

Overview: We will evaluate the feasibility and acceptability of our intervention (Persistence Targeted Smoking Cessation for Serious Mental Illness; PTSC-S) when delivered via telehealth in a single group, within-subjects design.. The purpose of this trial is to test the feasibility, acceptability, and initial efficacy of our PTSC-S intervention.

A. Participant Recruiting and Screening: The project will take place remotely via telehealth to reduce patient burden and travel difficulties. Our Rutgers offices in New Brunswick, NJ, are located in the building next to a large University Behavioral Health Care outpatient clinic that serves clients with serious and persistent mental illness. We will recruit New Jersey resident smokers from Rutgers University Behavioral Health Care, from the community via our website, social media, and local flyers, via Rutgers listservs, local

agencies or organizations who serve mental health consumers (i.e. CHOICES; Serv Behavioral Health Systems, Inc.; George J. Otlowski, Sr. Center for Mental Health Care, Hunterdon Behavioral Health Care), and ElevateU's Study Recruitment Platform (more detailed information listed below under "ElevateU Recruitment"). We will use IRB approved language from recruitment advertisements for electronic communication (i.e. listservs, newsletters, ect.) with approved study sites. Potential participants will call our offices for a telephone pre-screen or fill out an interest form on Qualtrics that would be followed by a telephone pre-screen. If potentially eligible, they will be offered a more in-depth telehealth phone or video assisted screening after providing informed consent. If all inclusion criteria are met, they will be invited to participate. This is an urban area with a large low-income population and therefore a greater proportion of smokers than the average of 14.8% in the state of New Jersey. Previous studies have given us the necessary experience with Rutgers listservs, websites, Craigslist, and use of flyers and brochures to maximize recruitment.

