In the event we are unable to meet with a patient using telehealth video services (e.g. because of internet connectivity issues), we will provide counseling using the telephone. There is a strong literature supporting tobacco "QuitLines", proactive telephone counseling and we would therefore still be providing treatment via an empirically supported format. We expect this will in the best interest of the patient as abruptly stopping treatment would be unethical.

Emails: We may create a Google account email with a complex password for each research participant using their assigned ID number and short title of our study "ptscs" (i.e. ID#[contact]) if a participant does not have an email address to use. We will store this information using the HIPAA compliant Microsoft OneDrive cloud storage system and may assist participants with their email as needed. No PHI will be transmitted via this email account. This email will be used to set up the Smokerlyzer application for the iCO Smokerlyzer device, as the application requires an email to be sent to our research team with the results of their breath test. We will ask our participants to not use this email account for communication outside of the research study to protect their confidentiality. See section 1.7.2 for more on the iCO Smokerlyzer device.

- B. Data Points:** We will collect data at baseline, at the end of treatment, and at follow up at 3-months post quit date.
- C. Duration:** Participants will be active in the study for approximately 4 months. We anticipate completing data collection activities within 32 months.
- D. Primary study endpoints** include baseline, at the end of treatment, and at follow up at 3-months post quit date. We will assess AEs on a rolling basis and report them at DSMB meetings. We will conduct an interim analysis after 50% of the target enrollment has completed followup assessment.

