2.2 Resources Available

Facilities- Participants will be daily smokers from New Jersey. Participants will attend treatment remotely using an online telehealth HIPAA compatible platform. Participants will be in the state of New Jersey during any counseling sessions though they may be outside of New Jersey (e.g., if they are traveling) for follow-up research assessment appointments.

Medical Or Psychological Resources- [name] is a licensed clinical psychologist in that state of New Jersey and will assist in training study staff in the management of crisis intervention. In addition, they will be available 24/7 to field any questions/concerns study staff have regarding how to proceed in the event that participants experience unanticipated psychiatric distress during the course of the study.

Research Staff Training- All graduate students and research assistants will complete intensive training with [name], including proper administration of each intervention condition and proper administration and management of nicotine replacement therapies. All graduate students will also complete weekly supervision with [name].

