4.3 Subject Randomization

N/A

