4.9 Risks to Subjects

A. Description of Subject Risk

There is a risk of discomfort associated with nicotine withdrawal for patients who are quitting smoking. The nicotine patch (an FDA-approved medication) is well tolerated; however, there are potential side effects that may arise when using the patch. Potential side effects include dizziness, headache, nausea, vomiting, diarrhea, or redness or swelling at the patch site. Each patient will discuss these side effects with their therapist. If questions arise as a result of the patch, one of the study co-investigators is an Addiction Psychiatrist who will be available to provide patients with information regarding their side effects.

The overall risk of AEs in this study is expected to be low because both the counseling sessions and the use of over-the-counter nicotine replacement products are low risk and similar to established treatments to help smokers quit. We will monitor patients for AEs at every session, however, and any AEs that are deemed to be moderate to severe will be reviewed by addiction psychiatrist, [name] and discussed at the weekly research meetings. The team will document the recommended actions with input from [name]. AEs will be followed until they resolve or until participant study completion. The AE Tracking Form and AE specifics log will also be completed.

There is a risk that participants' confidentiality could be violated. To reduce the risk of violating confidentiality, several steps will be taken. Only IRB approved members of the research team will have access to the data. All computers used by research staff will be password protected with complex passwords. The participants google email account will only include their participant ID number and we will ask that participants do not use this account for communication outside of the research study to protect their confidentiality. Data will only be accessed when coded, entered, or audited. The PI will maintain responsibility for safe data storage. All data will be stored in locked cabinets within locked rooms. We will use a telehealth platform that is HIPAA compatible (e.g. Microsoft Teams, Doxy.me, or zoom). Based on these procedures, we anticipate that the risk to confidentiality is very low.

B. Procedures for Risks to Embryo, Fetus, and/or Pregnant Subjects

N/A

C. Risks to Non-Subjects

N/A

D. Assessment of Social Behavior Considerations

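### Section 6.3 G's only adverse event analysis compares treatment groups, but the trial has one group, so it cannot be run and no single-cohort summary replaces it

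*Combined protocol and SAP*

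**What the plan says.** Section 6.3 G (Tests for Safety Data) contains a single sentence: "Independent t-tests will be used to examine differences between treatment groups with respect to number of adverse events reported".

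The design in the same document has no groups to compare. Section 1.3 states that the intervention will be evaluated "in a single group, within-subjects design". The section headed "4.3 Subject Randomization" is marked not applicable. The efficacy analyses in 6.1 A are paired comparisons with baseline.

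Two other places also read as if there were a second arm. Section 6.3 H allows early stopping if the interim analysis shows that the "PTSC-S intervention was more efficacious than the control intervention", and section 2.2 describes staff training "including proper administration of each intervention condition".

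Handling of individual adverse events is described in several places:
- Collection (6.3 C): "We will use case report forms to document adverse events at each telehealth patient contact".
- Reporting (1.3 D): "We will assess AEs on a rolling basis and report them at DSMB meetings".
- Clinical review (4.9): "any AEs that are deemed to be moderate to severe will be reviewed by addiction psychiatrist".

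Section 6.3 E adds that the principal investigator and the medical monitor look at safety data as it comes in.

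**The concern.** The one analysis of adverse events that the plan commits to requires two independent samples, and the trial will produce one. If nothing replaces it, the authors must decide after the data are in how to present safety: which denominator, which severity breakdown, and whether to attach an interval.

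The last choice matters most in a small study. Section 4.9 expects adverse events to be uncommon, so the likely result is a short list of events or none for some severities. A bare count of zero or three invites the reading that the treatment is safe. An interval shows how little a cohort of this size can exclude. The participants have serious mental illness, use nicotine patches for up to 10 weeks and are treated remotely, so readers will want a safety figure they can interpret.

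**Working it through.** **1. How many groups does the plan have?** The sample size section (1.5, repeated in 6.1 B) gives an independent check. Inputs: standardised within-person effect dz = 0.5, power 80%, alpha 0.05, and one-tailed paired t-tests (6.1 A). For a paired t-test on n participants, the power is the probability that a noncentral t variable with n − 1 degrees of freedom and noncentrality dz × √n exceeds the critical value.

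- At dz = 0.5, one-sided, the smallest n with at least 80% power is 27 (power 81.2%). This matches the stated 27.
- At dz = 1.28, one-sided, it is 6 (power 85.0%). This matches the stated 6.
- Allowing for 20% loss: 27 / (1 − 0.20) = 33.75, rounded up to 34. This matches the stated 34.

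The plan's figures are those of one paired group with no allowance for a comparator, which agrees with sections 1.3 and 4.3.

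**2. Can the 6.3 G test be computed?** The independent t statistic is

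t = (mean₁ − mean₂) / [s × √(1/n₁ + 1/n₂)], with n₁ + n₂ − 2 degrees of freedom.

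With n₁ = 34 and n₂ = 0, mean₂ does not exist and 1/n₂ is undefined. Running the test with an empty second group returns no statistic, no p-value and no degrees of freedom.

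**3. Does any other section supply a summary?**

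| Place | What it provides | Adverse event summary for one cohort? |
|---|---|---|
| 1.3 D | Rolling assessment, reports to the DSMB | No statistic stated |
| 1.6 B | Primary and secondary outcomes | Adverse events not listed |
| 1.9 B | Adverse event tracking form and log | Collection only |
| 4.9 | Clinical review of moderate to severe events | Case by case |
| 6.1 A | Descriptive statistics for Hypotheses 1a to 1c | Covers acceptability, follow-up and missing data only |
| 6.3 A to F | Collection, reviewers, review schedule | No statistic stated |
| 6.4 C | Examples of aggregate results | Adverse events not among them |

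None does. A few sections were not in the text available for review, so this holds for the available text.

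**4. What would a one-cohort summary show?** Use the exact (Clopper–Pearson) 95% interval for x participants with an event out of n. The lower limit is the 2.5% point of Beta(x, n − x + 1). The upper limit is the 97.5% point of Beta(x + 1, n − x). For x = 0 the upper limit reduces to 1 − 0.025^(1/n).

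- 0 of 34: 1 − 0.025^(1/34) = 0.103, so 0% to 10.3%.
- 3 of 34: 8.8%, interval 1.9% to 23.7%.
- 10 of 34: 29.4%, interval 15.1% to 47.5%.

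The event counts are illustrations, since the documents give no expected rate. The denominator of 34 is the recruitment target in 1.5. With only the 27 planned completers, the upper limit for zero events is 12.8%. With the 61 given in 4.1 and 4.5 C it is 5.9%.

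**The case against.** The best defence is that this is leftover wording in a low-risk feasibility study and harms nothing. Much of that stands. Adverse events are neither a primary nor a secondary outcome, no hypothesis uses them, and the treatment is counselling plus an over-the-counter patch. A carry-over from a controlled design is the likely explanation, given 6.3 H and 2.2, although that is inference. But this is the current text, and no workable analysis stands behind it. Correcting the wording means stating a summary.

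A second defence is that 6.3 G does name its variable, the number of adverse events, so a count survives once the comparison is removed. That is fair. A reader might infer that the safety results have no pre-specified content at all, and that goes too far. What is missing is the denominator, the severity breakdown and the interval.

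A third is that the groups might be earlier participants and the telehealth cohort, since 1.5 speaks of 34 additional participants while 4.1 gives 61. No section defines those groups or plans that comparison, and it would not be randomized. It does not rescue the test.

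Three stronger readings are tempting, and the documents support none of them:
- **That safety monitoring itself fails.** It does not. Capture at each contact, DSMB reporting and psychiatrist review can all be carried out. The adverse event part of the stopping rule in 6.3 H rests on the DSMB's judgement and does not use the 6.3 G test.
- **That events between contacts go unrecorded** because 6.3 C and D tie capture to contacts. The reference period would normally be printed on the form, and the forms are not reproduced. Section 1.9 B describes each in one sentence and schedules three post-baseline captures, and 4.9 follows events to resolution or study completion.
- **That dropout will make the adverse event figures too low by a calculable amount.** Any such figure needs event rates and last-contact times that the documents do not give, or a worst-case bound built on planned loss to follow-up. It would also be the same if 6.3 G were correctly written, so it does not measure this defect.

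**Conclusion.** The point holds. The plan's only stated adverse event analysis is impossible in a one-group trial, and the available text offers no single-cohort summary in its place. This follows from setting 6.3 G against 1.3 and 4.3, and rests on no statistical assumption.

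Its reach is limited to how cumulative safety data are summarised for the DSMB and reported. No efficacy or feasibility conclusion changes. The size of what an interval would add depends on the denominator: with no events, the 95% upper limit is 10.3% for 34 participants, 12.8% for 27 and 5.9% for 61. This should be corrected, but it does not threaten the trial's main conclusions.

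**What to change.** Replace the sentence in 6.3 G with a descriptive summary for the single cohort:

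- number and percentage of participants with at least one adverse event, overall and by severity, each with an exact 95% confidence interval and a stated denominator;
- total number of adverse events.

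State that this table goes to the DSMB and is reported with the results. No between-group test should remain.

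The cost is a wording change in 6.3 G and one simple table. The events are already recorded at each contact, and the review rule in 4.9 already implies a severity judgement. No new visits, staff or data are needed, and the downside is negligible.

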6.0 Research Data Protection and Reporting

6.1 Data Management and Confidentiality

A. Hypothesis 1: The PTSC-S intervention will be acceptable to participants, and the study will be feasible to conduct as evidenced by:

- a. At least 80% of participants will provide at least a 5 on a 1 – 7 scale regarding how “useful” the intervention was, how acceptable the length of each session was, and how acceptable the number of counseling sessions offered was (with higher scores reflecting ratings of more useful and more acceptable). Analysis 1a: Descriptive statistics will be reported.
- b. We will achieve follow-up rates of at least 80% at the 3-month follow-up. Analysis 1b: Descriptive statistics will be reported.
- c. Rates of missing/unusable data will be < 10% of all data collected. Analysis 1c: Descriptive statistics will be reported.

Hypothesis 2: As compared to baseline, participants will report greater task persistence as evidenced by reduced scores on the Thoughts About Smoking Questionnaire (TASQ). Analysis 2: One-tailed, paired sample t-tests will be used to examine decreases in scores on the TASQ at each timepoint.

Hypothesis 3: As compared to baseline, participants will report smoking fewer cigarettes per day at 1- and 3-month follow-up. Analysis 3: One-tailed, paired sample t-tests will be used to examine decreases in cigarettes smoked per day on the TASQ at each timepoint.

B. We determined the sample size based on data from the R21 phase of the study, we can expect a large effect (Cohen's $dz = 1.28$) of the intervention on task persistence as measured by the Thoughts About Smoking Questionnaire (TASQ). We detected a change in mean(SD) scores, in the predicted direction, from 4.371(1.0) at baseline to 3.218(1.1) at follow-up. An effect of $dz = 1.28$ setting power at 80% and alpha at 0.05 suggests we need $N = 6$ participants in the within-subjects analysis to detect an effect (see Figure 1 below).

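### Section 6.3 plans a between-group adverse event test and a stopping rule against a control, but the trial has one group; the halfway efficacy look also has no endpoint, test, boundary or defined 50%

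*Combined protocol and SAP*

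**What the plan says.** **Design.** Section 1.3 (Overview) evaluates PTSC-S "when delivered via telehealth in a single group, within-subjects design". The entry under "4.3 Subject Randomization" is N/A. In Section 6.1 A, Hypothesis 1 is handled descriptively. Hypotheses 2 and 3 are tested against baseline; for the TASQ, "One-tailed, paired sample t-tests will be used to examine decreases in scores on the TASQ at each timepoint".

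**Safety test.** Section 6.3 G: "Independent t-tests will be used to examine differences between treatment groups with respect to number of adverse events reported".

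**Efficacy stopping.** The last paragraph of Section 6.3 H stops the trial if the monitoring board concludes that the "interim analysis at the halfway point of the trial" gave "overwhelming evidence that PTSC-S intervention was more efficacious than the control intervention". The paragraph before it separately lets the board stop the trial for adverse events.

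**Timing of the look.** Section 1.3 D: "We will conduct an interim analysis after 50% of the target enrollment has completed followup assessment". Section 6.3 B: "Efficacy data will be evaluated after 50% of participants have completed follow-up data collection".

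**The concern.** A two-sample test needs two samples, and superiority over a control needs a control. The only test stated for safety data and the only efficacy-stopping rule both assume an arm that this trial does not have.

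Removing the comparator wording does not complete the plan. Section 6.3 G would then contain no safety analysis. Section 6.3 H would still attach stopping to a look whose endpoint, test and threshold are unstated, so those choices could be made after half the data have been seen.

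**Working it through.** **1. Is there a second group anywhere?**

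| Section | Implies |
|---|---|
| 1.3 Overview | one group, within-subject |
| 4.3 | no randomization |
| 1.5 and 6.1 B | sample size for a within-subject test |
| 6.1 A | paired tests against baseline |
| 6.3 G | at least two treatment groups |
| 6.3 H, last paragraph | a control intervention |

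Section 2.2 (staff training) also uses wording that suggests several conditions, but it names no second one.

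**2. Does the sample size confirm one group?** Inputs from Section 1.5: dz = 0.5, alpha 0.05, power 80%, 20% loss. The one-tailed paired test comes from Section 6.1 A. Power = P(T > t(0.95, n−1)), where T is noncentral t with n−1 degrees of freedom and noncentrality dz·√n.

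- dz = 0.5, one-sided: smallest n = 27, power 0.812. This matches the plan. Two-sided would need 34.
- dz = 1.28, one-sided: smallest n = 6, power 0.850. This matches the plan.
- Recruitment: 27/(1 − 0.20) = 33.75, rounded up to 34. This matches the plan.

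The plan's numbers are therefore those of a one-group, one-sided paired test at the full 0.05. They contain no second arm and no alpha set aside for an interim look.

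**3. Can G and H be computed?** The independent t statistic is (mean₁ − mean₂) / [s·√(1/n₁ + 1/n₂)]. With one group, mean₂ and n₂ do not exist and the statistic is undefined. The comparison in H fails for the same reason.

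**4. What is specified for the halfway look?**

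- Endpoint: not named. Prolonged abstinence is listed first among the primary outcomes (1.6 B) but has no analysis in 6.1 A. The TASQ carries Hypothesis 2, while task persistence is a secondary outcome. Cigarettes per day carries Hypothesis 3.
- Test and boundary: none. The only criterion is the verbal one in H.
- Follow-up visit: not named. Section 1.3 B lists end of treatment and 3 months post quit date.
- Denominator: no figure is labelled target enrollment. The protocol gives 34 additional recruits (1.5), 61 (4.1, and 4.5 C as the number required to complete), 90 (timetable, 1.10) and 120 in total (4.5 A). Their halves are 17, 30.5, 45 and 60.

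**5. Figures for the fix.**

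- *Exact 95% interval for adverse events.* With zero events the upper limit is 1 − 0.025^(1/n): 10.3% for n = 34 and 5.9% for n = 61. At 17/34, where the interval is widest, it is 32.4% to 67.6%. These show precision only; the documents give no expected event rate.
- *Interim p<0.001, final 0.05, one-sided.* The overall error cannot exceed 0.001 + 0.05 = 0.051. Simulation under the null with paired t-tests gave 0.0504 (17 then 34), 0.0503 (31 then 61) and 0.0501 (14 then 27). In the normal approximation, holding exactly 0.05 moves the final critical value only from 1.645 to 1.646.

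**The case against.** The strongest reply is that 6.3 G and H are leftover wording with no effect on what matters. Much of that stands. Adverse events are recorded at each contact, the investigator and medical monitor review them as they are collected, the board reviews them too, and its power to stop for adverse events needs no control. The analyses in 6.1 A do not use 6.3. G does not assign its test to the board, so a claim that safety oversight fails would go too far. But calling the wording leftover does not say what replaces it.

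Three stronger readings are tempting, and the documents do not support them.

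- *The interim look inflates type I error to about 8%.* A reader could get this by applying the one-tailed 0.05 test unadjusted at half and at full information: 1 − P(Z₁ ≤ 1.645, Z₂ ≤ 1.645) with correlation √0.5 is 0.080. The plan states no such rule. Its verbal standard suggests something stricter, and at p<0.001 the error stays at about 5%.
- *The look could fall anywhere from 17 to 60 participants.* This halves figures that may not be rivals: additional recruits, required completers, recruits in a timetable and total subjects. The 34 and 61 may be incremental and cumulative, and 120 may be a ceiling. The documents do not say, so what can be asserted is that the denominator is unlabelled and the figures need reconciling.
- *There are three conflicting triggers.* Sections 1.3 D and 6.3 B both mean half having completed follow-up, and H naturally refers back to that look. The wordings are compatible; the gaps are the denominator and the visit.

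Some pages are missing from the public text. A comparator defined there would contradict Sections 1.3 and 4.3, so reconciliation would still be needed.

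**Conclusion.** The contradiction is certain on the available text: one group, no comparator, and two rules in 6.3 (the test in G and the efficacy sentence in H) that cannot be carried out. The halfway efficacy look is also unspecified in endpoint, test, boundary, follow-up visit and denominator.

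The consequence is limited. The sample size and the baseline comparisons stand, and so does stopping for adverse events. No numerical bias or error inflation is claimed for the plan as written. It should be corrected before half the participants have been followed up, because after that the missing choices could be made with data in hand. The only assumption is that no unavailable page defines a second group.

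**What to change.** 1. **6.3 G.** Replace the between-group test with single-group summaries: number and percent of participants with at least one adverse event with an exact 95% interval, and event counts by severity.
2. **Halfway review (1.3 D, 6.3 B, 6.3 H).** Choose one route.
   - *Descriptive:* say so, and delete the control-based sentence in H.
   - *Efficacy look retained:* rewrite that sentence, rather than only deleting it, around one pre-specified within-subject endpoint, a paired test and an alpha-controlling boundary, for example interim p<0.001.
3. **1.3 D and 6.3 B.** State the N and the follow-up visit that define 50%, after reconciling 34, 61, 90 and 120.

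Leave the board's adverse-event stopping provision as it is.

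Cost: text edits, with no extra participants, visits or data. The descriptive route gives up a planned efficacy look and changes what the board is asked to do. The other route needs the endpoint, test and boundary agreed before any halfway data are seen.
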